1.2 OBJECTIVES

1.2.1 Primary objectives

The primary objective of this study is to evaluate the long-term safety and tolerability of dupilumab in patients with asthma who participated in a previous dupilumab asthma clinical study (DRI12544, EFC13579, EFC13691 or PDY14192).

1.2.2 Secondary objectives

To evaluate the long-term efficacy of dupilumab in patients with asthma who participated in a previous dupilumab asthma clinical study (DRI12544, EFC13579, EFC13691 or PDY14192).

To evaluate dupilumab in patients with asthma who participated in a previous dupilumab asthma clinical study (DRI12544, EFC13579, EFC13691 or PDY14192), with regards to:

- Systemic exposure
- Anti-drug antibodies
- Biomarkers

1.3 DETERMINATION OF SAMPLE SIZE

The study size is predicated on the overall size of the parent studies; hence, the maximum number of patients to participate will be the number corresponding to the sum of the total enrolled in DRI12544, PDY14192, EFC13579, and EFC13691 studies. Based on the actual patient number of

DRI12544 study and the planned patient numbers of EFC13579, EFC13691 and PDY14192 studies, the maximum number of patients of LTS12551 can be estimated as 2930.

1.4 STUDY PLAN

LTS12551 study consists of three periods, using an add-on therapy approach to inhaled corticosteroid (ICS) in combination with other acceptable controller medications maintained during the parent study, including the oral corticosteroids for the patients from the EFC13691 study.

Screening Period (0-3 weeks)

Patients are to be stabilized on their background dose of moderate or high-dose ICS for ≥ 1 month prior to Visit 1 and continue the stable dose during the screening period.

- The screening period is applicable for the patients from the DRI12544 study only.
- Eligible patients in PDY14192, EFC13579 or EFC13691 studies are to rollover into LTS12551 on the same day as the end of treatment visit in the parent study. Visit 1 and Visit 2 of LTS12551 study are combined with the end of treatment visit in the parent study for the patients enrolled from PDY14192, EFC13579 or EFC13691 studies, who start directly with the treatment period in the LTS12551 study.

Open-label Treatment Period (48 or 96 weeks)

During the open-label treatment period, patients continue their background controller therapy as maintained during the parent study or as modified based on investigator's judgment, including the oral corticosteroids for the patients from the EFC13691 study.

Post-treatment Period (12 weeks)

Upon completion of the open-label treatment period (or following early discontinuation of IMP) patients continue into the post-treatment period. During this period, patients continue with the background controller therapies as maintained during the open-label treatment period or as modified based on investigator's judgment.

Reliever Medications

Over the course of LTS12551 study, patients may receive salbutamol / albuterol hydrofluoroalkane pressurized MDI or levosalbutamol / levalbuterol hydrofluoroalkane pressurized MDI as reliever medication as needed. Nebulizer solutions with either albuterol / salbutamol or levalabuterol / levosalbutamol may be used as an alternative delivery method.

Statistical Analysis Plan SAR231893-LTS12551 - dupilumab 20-Jul-2017 Version number: 3

1.4.1 Graphical Study Design

1.5 MODIFICATIONS TO THE STATISTICAL SECTION OF THE PROTOCOL

Amendment Number	Date Approved	Rationale	Description of statistical changes
4	31-Oct- 2016	Based on the data defining the safety profile of dupilumab to date (as determined in multiple clinical trials performed across the AD, Asthma and NP indications), data from a 1 year asthma OLE study is anticipated to be sufficient to support the asthma program.	The open-label treatment duration is amended to 48 weeks (1 year), for patients providing consents after the implementation of the protocol amendment 4.
4	31-Oct- 2016	The DRI12544 study showed that the median dupilumab concentration at 12 weeks post-last-dose (at PK steady-state) was below the limit of quantitation (78 ng/mL) for the group of patients on 300 mg every 2 weeks (q2w). Given this, the duration of study participation can be minimized by reducing the post-treatment period by 1 month. The follow-up duration for all the ongoing dupilumab asthma studies has been harmonized as 12 weeks.	The post-treatment period is shortened to 12 weeks for all patients in the LTS12551 study.
4	31-Oct- 2016	The patient population from study EFC13691 is a different population from the patient population from the other parent studies. The patients from	Three efficacy endpoints linked to the prescribed oral corticosteroids (OCS) dose and corresponding analyses have been added only for the patients from the EFC13691.

Table 1 - Protocol amendment statistical changes

Amendment Number	Date Approved	Rationale	Description of statistical changes
		EFC13691 are more severe at the baseline of the parent study and are using a different background controller medication. The endpoints linked to the reduction of the OCS dose are only used in EFC13691, in addition to the other efficacy endpoints shared in common with the patients from the other parent studies.	

1.6 STATISTICAL MODIFICATIONS MADE IN THE STATISTICAL ANALYSIS PLAN

This statistical analysis plan (SAP) version 3.0 is based on the LTS12551 amended protocol 2 (protocol amendment 4) dated October 31st, 2016, and is the third version of SAP for LTS12551.

SAP version number	Date approved	Rationale	Description of statistical changes
2	23-Nov-2016	Protocol amendment 4 shortens the open-label treatment period to 48 weeks.	The open-label treatment duration is amended to 48 weeks for patients providing consents after the implementation of the protocol amendment 4.
2	23-Nov-2016	Protocol amendment 4 drops the electronic diary, PEF meter, EQ-5D-3L, serum immunoglobulins, and serum total IgE for all the patients in LTS12551 study. Before the protocol amendment 4 becomes effective, the patients from	The analyses for AM/PM PEF, AM/PM asthma symptom score, number of reliever uses, number of nocturnal awakenings, EQ-5D-3L score, serum immunoglobulins and serum total IgE in LTS12551 study will be restricted to the patients from the DRI12544 study and performed to the data observed up

SAP			
version	Date		
number	approved	Rationale	Description of statistical changes
		DRI12544 study have data collection for the aforementioned endpoints for more than one year, while only a few of patients from EFC13579, EFC13691 or PDY14192 studies have limited amount of data collected for those endpoints.	to the end of their collection. The compliance for background controller medications will be calculated using the data observed up to the end of the electronic diary collection.
2	23-Nov-2016	Protocol amendment 4 adds three efficacy endpoints linked to the prescribed OCS dose for the patients from the EFC13691 study only. They are the percentage change from baseline in the OCS dose, the proportion of patients achieving a reduction of 50% or greater in the OCS dose compared with the baseline, and the proportion of patients whose background OCS are completely tapered off. The baseline OCS dose is defined as the original baseline value of the parent study.	The proportion of patients whose background OCS are completely tapered off and its analysis have been added to this version of SAP, and the other two endpoints linked to the OCS dose and their corresponding analyses have already existed in the SAP 1.0.
2	23-Nov-2016	Protocol amendment 4 reduces the frequency of assessments for the ACQ-5, AQLQ, clinical laboratories, ECG and ADA variables for all patients in the LTS12551 study.	The scheduled visits and corresponding analysis windows for the endpoints of ACQ-5, AQLQ, clinical laboratories, ECG and ADA are adjusted accordingly per the reduced scheduled visits in the protocol amendment 4.
2	23-Nov-2016	The patient population from study EFC13691 is expected to be different from the	All the planned analyses in LTS12551 study will be performed and presented separately for the

Statistical Analysis Plan SAR231893-LTS12551 - dupilumab

SAP	Data		
number	approved	Rationale	Description of statistical changes
		patient population from the DRI12544, EFC13579 or PDY14192 studies. The patients from EFC13691 are more severe at the baseline of the parent study and are using a different background controller medication, and thus potentially have different safety profiles in general from the patient population from the other parent studies.	patients from EFC13691 study and the patients from DRI12544, EFC13579 or PDY14192 studies, except for the endpoints that are particularly collected for the patients from EFC13691 study only.
3	This version	The layouts of all outputs are changed to avoid potential confounding introduced by between-study variation.	The treatment category (Naïve, Re- treated, Interrupted treatment, and Continuously treated) is removed.
			The layouts of all outputs are changed to:
			For the patients from EFC13691 study, results of each planned analysis will be presented by "Placebo/Dupilumab, Dupilumab/Dupilumab, and All" (see Section 2.3.2).
			For the patients from DRI12544/EFC13579/PDY14192 studies, results of each planned analysis will be presented by the parent study and "All", and by "Placebo/Dupilumab and Dupilumab/Dupilumab" within each parent study (see Section 2.3.2).
3	This version	To be consistent with ISS SAP	The definition of AESI and other selected AE groupings are updated in Section 2.1.4.1

Property of the Sanofi Group - strictly confidential

Page 15

SAP version	Date		
number	approved	Rationale	Description of statistical changes
3	This version	To be consistent with ISS SAP by including the combined PCSA criteria for adult and adolescents	PCSA criteria in Appendix A are updated
3	This version	To be consistent with the amended protocol #2 of LTS12551 study	The lab test parameters lactate dehydrogenase, low-density lipoprotein, high-density lipoprotein, and triglycerides are removed according to the amended protocol #2 of LTS12551 study
3	This version	To be consistent with EFC13579 / EFC13691 studies	The definition of persistent ADA response is updated in Section 2.1.6
3	This version	To be consistent with EFC13579 / EFC13691 studies	The definitions of Comorbidity history and Atopic Medical History are updated in Section 2.1.1
3	This version	Add additional subgroup analyses	The subgroup defined by the eosinophil count at baseline of parent study is added to the subgroup analysis for key efficacy endpoints in Section 2.4.4.1.
			The subgroup defined by the Ethnicity at baseline of parent study is added to the subgroup analysis for key safety endpoints in Section 2.4.5.6.

2 STATISTICAL AND ANALYTICAL PROCEDURES

2.1 ANALYSIS ENDPOINTS

In general, the baseline values of endpoints in LTS12551 are correspondingly defined as the original baselines of the parent studies, unless otherwise specified. In addition to the baselines, the pre-dose measurements at Week 0 of LTS12551 are defined as follows. For patients enrolled from DRI12544, the measurements at Week 0 are obtained from the EOS visit of DRI12544 if available, regardless of whether the EOS visit in DRI12544 was combined with Visit 1/Visit 2 in LTS12551; otherwise, Week 0 value will be the last available measurement prior to the first IMP dose in LTS12551 study. For patients enrolled from the EOT visit of the parent studies if available; otherwise, Week 0 value will be the last available measurement prior to the first IMP dose in LTS12551 study.

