PDY14192: A phase 2a, exploratory, randomized, double-blind, placebo-controlled study of the effects of dupilumab 300 mg q2w SC for 12 weeks on airway inflammation of adults with persistent asthma. Patients are randomized in a ratio of 1:1 to dupilumab 300 mg q2w and placebo q2w. Patients undergo two bronchoscopy procedures respectively before treatment and at the end of treatment period, each of which is followed with an oral prednisone 40 mg daily treatment for 3 (up to 5) days. Patients are allowed to administer a background therapy of medium to high dose ICS in combination with a second controller medication (LABA), and potentially plus a third controller medication (eg, LAMA, LTRA). There are in total 42 patients planned for PDY14192.

Parent study	Sample size	Treatment arms	Treatment duration	
		Dupilumab 300 mg q2w,		
		Dupilumab 200 mg q2w,	24 weeks	
DRI12544	776	Dupilumab 300 mg q4w,		
		Dupilumab 200 mg q4w,		
		Placebo q2w (2 mL in matched 5 mL vials)		
	1902	Dupilumab 300 mg q2w,		
EEC12570		Placebo q2w matching 300 mg q2w (2 mL in matched pre-filled syringe),	52 weeks	
EFC15579		Dupilumab 200 mg q2w,	J2 WEEKS	
		Placebo q2w matching 200 mg q2w (1.14 mL in matched pre-filled syringe)		
EFC13691	210	Dupilumab 300 mg q2w, Placebo q2w (2 mL in matched pre-filled syringe)	24 weeks	
PDY14192	42	Dupilumab 300 mg q2w, Placebo q2w (2 mL in matched pre-filled syringe)	12 weeks	

Patients from DRI12544 who completed the 24-week treatment period and 16-week follow-up period might be eligible for enrolling into LTS12551 at the end of study (EOS) visit of DRI12544 or thereafter. The screening period (Visit 1 and Visit 2) of LTS12551, and a 600 mg loading dose on Day 1 were only applicable for patients coming from DRI12544, as those patients experienced a gap in dosing for at least 16 weeks. According to the original protocol of LTS12551, patients coming from DRI12544 (non-US) could combine the EOS visit of DRI12544 with Visit 1/Visit 2 of LTS12551; according to the amended protocol 1, Visit 1 and Visit 2 of LTS12551 should be independent from the EOS visit of DRI12544. Thus, after the protocol amendment 1 became effective in LTS12551, patients from DRI12544 should be screened starting at Visit 1 (for 7 to 21 days) in LTS12551 before dosing started at Visit 2.

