2.4.4 Analyses of efficacy endpoints

There will be no confirmatory analysis for the efficacy variables. All analyses will be done descriptively on the safety population in observed case, as appropriate. The baseline value for efficacy parameters is the original baselines from the parent studies.

For severe exacerbation events, the number of patients with one or more severe exacerbation events (number and qualitative variable: Yes/No), number of severe exacerbation events (qualitative variable: 0, 1, 2, 3, \geq 4), total number of severe exacerbation events, total patient-years, unadjusted annualized severe exacerbation event rate, and individual patient annualized severe exacerbation event rate (number, mean, SD, median, minimum, maximum) will be presented by the treatment category and overall (see Section 2.3.2) during the treatment period. Number and annualized rate will also be analyzed for severe exacerbation with use of systemic corticosteroids for \geq 3 days only, and that with hospitalization or with emergency room visit only. The mean duration of a severe exacerbation will also be summarized.

For the continuous efficacy variables listed in Section 2.1.3, descriptive statistics (mean, SD, median, minimum and maximum) will be presented for the parameter and its change from baseline over visits and by the treatment category and overall (see Section 2.3.2). In addition, figure of mean change from baseline (with corresponding standard error) will be presented for the continuous efficacy parameter over visits and by the treatment category and overall (see Section 2.3.2).

For the categorical efficacy variables listed in Section 2.1.3, the number and percentage will be presented over time for all patients who have data available at that time point by the treatment category and overall (see Section 2.3.2).

In addition, particularly for the patients coming from the EFC13691 study, the descriptive statistics (mean, SD, median, minimum and maximum) for the percentage change from baseline in oral corticosteroids (OCS) dose will be presented over time by the treatment category and overall (see Section 2.3.2); and, the proportion of patients achieving a reduction of 50% or greater in their OCS dose compared with the original baseline in parent study, and the proportion of patients whose background OCS are completely tapered off will be presented over time by the treatment category and overall (see Section 2.3.2).

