2.4.5.3 Analyses of laboratory variables

The baseline value of all laboratory variables is the original baseline from the parent studies. The pre-dose measurement at Week 0 of LTS12551 will be separately presented in the summaries or plots over time. This section will be organized by biological function as in Section 2.1.4.3.

The summary statistics (including number, mean, median, standard deviation, Q1, Q3, minimum and maximum) of all laboratory variables (central laboratory values and changes from baseline) will be calculated for each visit or study assessment (baseline, each post-baseline time point, and endpoint) by the treatment category and overall (see Section 2.3.2).

For all laboratory variables, the mean change from baseline with corresponding standard error at each visit will be plotted by the treatment category and overall (see Section 2.3.2).

For all laboratory variables, the summary statistics over visits for either measurements or mean change from baseline, and the plot of mean change from baseline over visits should use the centralized data only, and should include the measurements obtained at either scheduled or unscheduled visits.

The incidence of PCSAs (list provided in Appendix A) at any time during the treatment-emergent adverse event period will be summarized by biological function, and by the treatment category and overall (see Section 2.3.2), regardless of the baseline level and/or according to the following status at baseline of parent study and at Week 0 of LTS12551 study, respectively:

• Normal/missing

• Abnormal according to PCSA criterion or criteria

For parameters for which no PCSA criterion is defined, similar table(s) using the normal range will be provided.

For PCSA analyses, the laboratory measurements obtained at either scheduled or unscheduled visits should be used; and, both the centralized and local test results should be used, as long as their available dates/time is different from each other's. Centralized data will be used preferentially to the local measures in the PCSA analyses when measurements are performed on the same date and at the same time for a given laboratory test.

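### For DRI12544 patients the SAP takes Week 0 from the parent end-of-study visit even when a later pre-dose LTS12551 value exists, so Week 0 status in the PCSA and shift tables can be out of date

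*SAP*

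**What the plan says.** SAP 2.1 sets a Week 0 value alongside the baseline. For DRI12544 patients, "the measurements at Week 0 are obtained from the EOS visit of DRI12544 if available". This holds whether or not that visit doubled as the LTS12551 entry visit. Only if no such value exists does the second clause apply: "otherwise, Week 0 value will be the last available measurement prior to the first IMP dose in LTS12551 study". SAP 2.4.5 and 2.5.4 repeat the rule.

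SAP 1.1 describes how these patients entered. They "might be eligible for enrolling into LTS12551 at the end of study (EOS) visit of DRI12544 or thereafter". Under the original protocol, non-US patients could combine the two visits. Under amended protocol 1, "Visit 1 and Visit 2 of LTS12551 should be independent from the EOS visit of DRI12544", and screening at Visit 1 ran for 7 to 21 days before dosing at Visit 2.

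Week 0 is not the analysis baseline. SAP 2.1 says that "the baseline values of endpoints in LTS12551 are correspondingly defined as the original baselines of the parent studies, unless otherwise specified", and SAP 2.4.4 repeats this for efficacy: "The baseline value for efficacy parameters is the original baselines from the parent studies". Week 0 does enter the PCSA tables. SAP 2.4.5.3 splits incidence "according to the following status at baseline of parent study and at Week 0 of LTS12551 study", and SAP 2.4.5.4 and 2.4.5.5 do the same for vital signs and ECG. Protocol 11.4.3.1.4 adds shift tables against both baseline and Week 0. SAP 2.4.5 shows Week 0 in the by-visit summaries and figures.

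**The concern.** A value labelled pre-dose should describe the patient as close to the first dose as the data allow. Here an older value outranks a newer one by rule, and the SAP gives no reason for the preference. The rule also cuts across the SAP's own visit windows: Table 5 lets Week 0 run up to the date and time of the first dose, yet a later value inside that window is set aside.

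What is at stake is the Week 0 split in safety tables, in a study whose primary objective is safety. Suppose a laboratory value was normal at the parent EOS visit, abnormal at LTS12551 Visit 1, and still abnormal on treatment. That patient is shown as normal or missing at Week 0 with a PCSA after dosing. For DRI12544 patients the SAP also records AEs from consent and tabulates pre-treatment AEs. The same finding could therefore be a pre-treatment event in one table and an apparently new abnormality in another.

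**Working it through.** The documents state no figure that depends on the Week 0 rule, so there is nothing of that kind to reproduce. The check is whether a later value can exist, where Week 0 is used, and what a different rule would change.

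**1. Can a later pre-dose value exist?** Yes. The SAP schedules spirometry (2.1.3.2), laboratory samples (2.1.4.3) and ECG (2.1.4.5) at Visit 1, and vital signs at every scheduled visit (2.1.4.4). After amendment 1, Visit 1 was separate from EOS and at least 7 days before dosing. Because entry could be at EOS or later, the EOS-to-dose gap has a minimum of 7 days for those patients and no stated maximum. Where EOS was combined with Visits 1 and 2 on the dosing day, the gap is 0 and the rule makes no difference.

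**2. Where is Week 0 used?**

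| Output | Reference | Depends on Week 0? |
|---|---|---|
| Change from baseline: efficacy, laboratory, vital signs, ECG, PD | Original parent baseline | No |
| TEAE n (%), primary endpoint | Timing of event against first dose | No |
| PCSA incidence irrespective of baseline, or by parent-baseline status | None, or parent baseline | No |
| PCSA incidence by Week 0 status (SAP 2.4.5.3 to 2.4.5.5) | Week 0 | Yes |
| Week 0 shift tables (Protocol 11.4.3.1.4) | Week 0 | Yes |
| Week 0 point in by-visit tables and figures (SAP 2.4.5) | Week 0 | Yes |

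Week 0 PEF (SAP 2.1.3.6.1) and Week 0 PK (SAP 2.4.6.1) have their own derivations.

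**3. Effect on differences.** Let B be the parent baseline, E the EOS value, S the later pre-dose value and P a post-dose value.
- Change from baseline is P − B under either rule, so the two rules differ by 0.
- A reader's Week 0-to-post difference is P − E under the SAP rule and P − S under a last-pre-dose rule. These differ by (P − E) − (P − S) = S − E.
- With made-up values B = 2.0, E = 2.3, S = 2.1 and P = 2.4, change from baseline is 0.4 under both rules. The Week 0-to-post difference is 0.1 against 0.3, a difference of −0.2 = S − E.

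**4. Effect on the Week 0-normal stratum, as an illustration.** Let q be the share of EOS-normal patients who become abnormal before dosing and stay so, and r the true rate of new PCSAs after dosing. Neither is in the documents; both are assumed. The apparent rate is q + (1 − q)r. With r = 5%:
- q = 1%: 0.01 + 0.99 × 0.05 = 0.0595, about 6.0%
- q = 2%: 0.02 + 0.98 × 0.05 = 0.0690, 6.9%
- q = 5%: 0.05 + 0.95 × 0.05 = 0.0975, about 9.8%

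This covers one direction only. In the other, a patient abnormal at EOS who is normal again by Visit 1 sits in the Week 0-abnormal stratum. A later recurrence is then read as pre-existing and leaves the normal stratum.

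**5. How many patients?** SAP 1.1 gives 776 enrolled in DRI12544. The parent sizes sum to 776 + 1902 + 210 + 42 = 2930, which matches the maximum in SAP 1.3. The ceiling is therefore 776/2930 = 26.5%, or 776/2206 = 35.2% of the approximate total in the protocol synopsis. Neither is an estimate: the documents do not give the number who rolled over, the number screened under amendment 1, or the actual gaps.

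**The case against.** A reader might infer that this rule credits or charges dupilumab with changes that happened before dosing throughout the study. The documents do not support that. Week 0 is additional to the baseline, every planned change-from-baseline analysis uses the parent baseline, and the primary endpoint is decided by event timing. Total PCSA counts do not move either: a PCSA counts if it is seen in the treatment-emergent period, and criteria with a change component refer to the parent baseline. A different Week 0 rule only moves patients between Week 0 strata.

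Four further points can be made for the SAP.

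- The wording shows that the choice was deliberate, and it anchors each parent study to its last parent visit (EOS for DRI12544, EOT for the others). That is a consistent convention, but the SAP gives no reason for preferring it to a newer value.
- EOS is itself an off-drug measurement, taken after the 16-week parent follow-up, so no systematic drift between EOS and Visit 1 need be expected. This stands, but individual misclassification does not need drift.
- The error can go either way, and where it makes an old abnormality look new it errs towards caution about the drug. This also stands, and it rules out claiming a bias in one direction.
- Results are shown by parent study (SAP 2.3.2), so any effect is confined to the DRI12544 columns and the pooled column. That limits its reach, but within the DRI12544 columns it is not diluted by the other studies.

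**Conclusion.** The point holds in a limited form. For DRI12544 patients with a gap between EOS and the first LTS12551 dose, the SAP sets aside a later pre-dose value wherever an EOS value is available. Patients can then be misclassified, in either direction, in the Week 0-stratified PCSA tables, the Week 0 shift tables and the Week 0 point of by-visit displays. Nothing else in the plan is affected.

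The size cannot be calculated from the documents. The 776 patients are parent enrolment and so only a ceiling. Patients whose visits were combined on the dosing day, and those with no EOS value, are not affected. The rates of 6.0% to 9.8% against 5% show the mechanism under assumed inputs and are not estimates for this trial. The conclusion rests on the Visit 1 assessments having been done as scheduled.

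This is a low-cost improvement to the safety tables and does not threaten the study's main results.

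**What to change.** In SAP 2.1, 2.4.5 and 2.5.4 together, replace the Week 0 rule with one definition for all parent studies: the last available measurement at or before the date and time of the first LTS12551 dose, with the parent EOS or EOT value used when it is that last value. State that the separate Week 0 rules for PEF (2.1.3.6.1) and PK (2.4.6.1) are unchanged.

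This extends the SAP's existing fallback, uses measurements already scheduled and needs no new data. Patients whose EOS or EOT value is their last before dosing keep the same Week 0 value.

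The cost is small. Week 0 for DRI12544 would no longer always be tied to the parent rollover visit, and any Week 0 tables already produced for an interim report may differ slightly. If the sponsor prefers to keep the present rule, it should give the reason and tabulate the EOS-to-first-dose gap for DRI12544 patients.
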